9. STATISTICAL CONSIDERATIONS AND DATA ANALYSES

A statistical analysis plan (SAP) will describe the detailed statistical methods and analyses for this study. The SAP will be prepared and finalized prior to unblinding of patients' study treatment assignments.

All hypothesis tests and confidence intervals will be 2-sided at an alpha level of 5%. Methodology to be used to maintain study-wide type I error rate of 5% across primary and secondary endpoint testing will be described in the SAP.

All efficacy and safety measures over the course of the study will be presented. Continuous data will be summarized by means, standard deviations, medians, maximum, minimum, and number of patients. Categorical data will be summarized by counts and percentages.

9.1. Randomization Methods

Central randomization will be used and treatment allocation will be 1:1:1 to relugolix plus low-dose hormonal add-back therapy (Group A), relugolix monotherapy plus placebo followed by relugolix plus low-dose hormonal add-back therapy (Group B), and placebo (Group C).

Randomization will be stratified by the following factors:

- Geographic Region: North America versus Rest of World; and
- Mean screening menstrual blood loss using alkaline hematin method: < 225 mL versus \geq 225 mL.

Statistical analyses for all efficacy endpoints will incorporate these stratification factors unless otherwise specified.

9.2. Analysis Populations

The Intent-to-Treat (ITT) Population will consist of all patients randomized to treatment who have taken at least one dose of study treatment. This will be the primary population used for the efficacy analysis.

The Per-Protocol Population will consist of those members of the ITT Population who have no major protocol violations. The Per-Protocol Population will not be analyzed if this population comprises more than 95% or less than 50% of the ITT Population. This population will be used for confirmatory analysis of the primary efficacy endpoint. The Per-Protocol Population will be identified prior to breaking the study blind.

The primary population for safety analyses will be the Safety Population, which will consist of all patients who are randomized and took at least one dose of study treatment.

9.3. Efficacy Analyses

Inferential efficacy assessments will be made between the following groups and 24 Weeks of placebo:

- Relugolix Group A: 24 weeks of oral relugolix 40 mg once daily co-administered with low-dose estradiol and norethindrone acetate;
- Relugolix Group B: 12 weeks of oral relugolix 40 mg once daily followed by 12 weeks of oral relugolix 40 mg once daily co-administered with low-dose estradiol and norethindrone acetate.

Descriptive characterization of treatment effect will be assessed between both relugolix groups.

9.3.1. Primary Endpoint Analysis

The primary endpoint is the proportion of women in the relugolix Group A versus the placebo Group C who achieve both a menstrual blood loss volume of < 80 mL AND at least a 50% reduction from baseline in menstrual blood loss volume over the last 35 days of treatment as measured by the alkaline hematin method.

Baseline menstrual blood loss is defined as the average menstrual blood loss from the two Screening menstrual cycles used to meet the inclusion criteria prior to the date of the first dose of study drug as assessed by the alkaline hematin method. The menstrual blood loss during the final study month is the total menstrual blood loss during the last 35 days on treatment as assessed by the alkaline hematin method. The treatment comparison between the relugolix Group A and the placebo Group C will be analyzed using a Cochran-Mantel-Haenszel test statistic for stratified proportions. The differences between the relugolix Group A and placebo Group C and 2-sided 95% confidence intervals will be estimated based on stratum-adjusted Mantel-Haenszel proportions.

Patients who discontinue the study before Week 4 (28 days) will be considered as treatment failures for the primary endpoint. The primary analyses will be based on the ITT Population. In addition, analyses of the Per-Protocol Population will be used to support the primary efficacy analysis. Details will be provided in the SAP. Additional missing data imputations will be conducted as sensitivity analyses to support the primary analysis. Details will be provided in the SAP.

For the assessment of the superiority of relugolix Group A versus placebo Group C in the proportion of patients who achieve both a menstrual blood loss volume of < 80 mL AND at least a 50% reduction in menstrual blood loss volume over the last 35 days of treatment, a sample size of ~130 patients in the relugolix Group A versus ~130 in the placebo Group C will provide greater than 99% power to detect a difference of greater than 30% using a 2-sided test at significance level of 0.05. The study will enroll 3 groups with a targeted 130 patients in each group for a total sample size of 390.

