3. STUDY OBJECTIVES AND ENDPOINTS

Inferential efficacy assessments will be made between the following groups and placebo Group C after 24 weeks of study treatment:

- Relugolix Group A: 24 weeks of oral relugolix 40 mg once daily co-administered with 1.0 mg estradiol and 0.5 mg norethindrone acetate;
- Relugolix Group B: 12 weeks of oral relugolix 40 mg once daily followed by 12 weeks of oral relugolix 40 mg once daily co-administered with 1.0 mg estradiol and 0.5 mg norethindrone acetate.

Descriptive assessment of treatment effect will be made between each relugolix group (Group A and Group B) and placebo (Group C) for safety outcomes and between each of the two relugolix groups for both efficacy and safety.

Objective(s)	Endpoint(s)
Primary Efficacy	

 • To determine the benefit of relugolix 40 mg once daily co-administered with low-dose estradiol and norethindrone acetate compared with placebo for 24 weeks on heavy menstrual bleeding associated with uterine fibroids. 	
 • Proportion of women in the relugolix Group A versus the placebo Group C who achieve a menstrual blood loss volume of < 80 mL AND at least a 50% reduction from baseline menstrual blood loss volume over the last 35 days of treatment, as measured by the alkaline hematin method.
Secondary Efficacy	

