4.6. Removal of Patients from Therapy

Completion of the Week 24 defines completion of the study. Patients may withdraw consent to participate in the study and discontinue treatment at any time for any reason. Investigators or the medical monitor may remove patients from therapy under this protocol for reasons of safety and/or lack of compliance as discussed below. Patients removed from therapy for any reason will undergo the assessments for the Early Termination visit (Week 24 visit) on the Schedule of Activities and will have a Follow-up visit to assess safety approximately 30 days after the end of study drug treatment (ie, after the patient's last dose of study medication).

The following safety and/or compliance events will result in the removal of patients from therapy either permanently or until the etiology of the problem has been identified and resolved:

- Any adverse event that is intolerable to the patient and that cannot be ameliorated by the use of adequate medical intervention, or that in the opinion of the investigator or medical monitor would lead to undue risk to the patient if dosing continued;
- If it is discovered after randomization that a patient failed to meet protocol entry criteria and continued participation poses an unacceptable risk to the patient's health;
- If the following liver test abnormalities develop, study drug should be discontinued immediately with appropriate clinical follow-up (including repeat laboratory tests, until a patient's laboratory profile has returned to normal/baseline status):
 - ALT or AST > 8 x ULN; or
 - ALT or AST > 5 x ULN and persists for more than 2 weeks; or
 - ALT or AST > 3 x ULN in conjunction with elevated total bilirubin > 2 x ULN or international normalized ratio (INR) > 1.5; or
 - ALT or AST > 3 x ULN with appearance of fatigue, nausea, vomiting, right upper quadrant pain or tenderness, fever, rash and/or eosinophilia (> 5%);
- Corrected QTcF prolongation of more than 500 msec as read by a cardiologist;
- Patients who have a clinically significant decrease in visual acuity as evaluated by an ophthalmologist;
- Patients who are, in the opinion of the investigator or the medical monitor, grossly non-compliant with the protocol's requirements;
- If the patient becomes pregnant at any time after providing a signed informed consent form, the patient must be withdrawn immediately (see [Section 7.8](#) for information on pregnancy reporting).

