6.7. Study Procedures

6.7.1. Efficacy-Related Procedures

6.7.1.1. Menstrual Blood Loss as Assessed by the Alkaline Hematin Method

The volume of menstrual blood loss is measured in milliliters using the alkaline hematin method [[Hallberg, 1964](#)]. The method involves pummeling used feminine products in a solution and measuring the resulting hematin absorbance against calibration curves. The method is validated in accordance with current FDA Guidance for Method Validations and is an accepted quantitative clinical endpoint for the assessment of heavy menstrual bleeding. The site staff will provide collection kits with standardized and validated feminine products to patients for the collection and assessment of those products to determine menstrual blood loss.

The feminine products will be dispensed and collected at each visit until the patient completes treatment or terminates participation from the study prior to completing treatment. Each time the patient submits her feminine products from a menstrual cycle for analysis, a venous blood sample will be collected and sent to the laboratory. Details regarding materials, process, and requirements for the menstrual blood loss collection will be provided in the Study Reference Manual.

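### The 28-day failure cut-off does not match the 35-day response window, and a window not tied to Week 24 lets later drop-outs count as responders for a 24-week objective

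*Protocol*

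**What the plan says.** Section 9.3.1 gives one discontinuation rule for the primary endpoint: "Patients who discontinue the study before Week 4 (28 days) will be considered as treatment failures for the primary endpoint". It defines the measurement by a different length and a different clock: "The menstrual blood loss during the final study month is the total menstrual blood loss during the last 35 days on treatment". A responder needs less than 80 mL and at least a 50% fall from baseline in that window.

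The time frame elsewhere is 24 weeks. The primary objective in Section 3 is benefit "compared with placebo for 24 weeks on heavy menstrual bleeding associated with uterine fibroids", and the same section says "Inferential efficacy assessments will be made between the following groups and placebo Group C after 24 weeks of study treatment". Section 4.6 adds: "Completion of the Week 24 defines completion of the study".

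Early leavers do supply data. Under Section 6.7.1.1, feminine products are "dispensed and collected at each visit until the patient completes treatment or terminates participation from the study". Section 6.5 gives the Early Termination visit the same procedures as Week 24, apart from some exemptions for imaging and biopsy. Section 9.3.1 mentions further imputation only as sensitivity analysis and leaves details to the SAP. Section 9.3.1 appears twice in the file, and both copies carry these rules.

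**The concern.** There are two separate problems.

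**Mismatch.** A woman who stops on Days 28 to 34 falls between the rules. She is past the failure cut-off but has not had 35 treated days. The text gives no other rule for her, so she would be scored on a shortened window. On placebo, where cycles continue, that window can end before her next menses, and she can pass for lack of observation time.

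**Floating window.** A woman who stops later is scored on whatever her last 35 treated days were. If she stops at Week 10 for an adverse event, she can be a responder for an objective framed over 24 weeks. The planned imputations do not reach her, because her window is observed and nothing is missing.

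At stake is the meaning of the primary responder rate. Section 9.3.2 applies the same method to the Group B responder endpoint. There, a woman who stops before Week 12 would be judged on relugolix without add-back.

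**Working it through.** **Inputs**
- Cut-off of 28 days and window of 35 days: Section 9.3.1.
- Eligible cycles of 21 to 38 days: Section 4.3.1, criterion on regular periods.
- 130 per arm, 30-point difference, two-sided 0.05, power above 99%: Section 9.3.1.
- Placebo response of 25%: Protocol Synopsis, Sample Size (Section 9.3.1 does not repeat it). Group A is then 25% + 30 points = 55%.
- Drop-out after Week 4: no figure found. The values below are assumptions.

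**1. The plan's own power**

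Power = Φ{[Δ − 1.96·√(2p̄(1−p̄)/n)] / √([p₁(1−p₁)+p₂(1−p₂)]/n)}

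With 0.25, 0.55 and n = 130: p̄ = 0.40, Δ = 0.30. The numerator is 0.300 − 1.96 × 0.0608 = 0.181 and the denominator is 0.0578. The ratio is 3.13, so power is 99.91%. The stated figure reproduces.

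**2. The gap**

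Shortfall = 35 − treated days. Stopping on Day 28, 29, 30 or 34 leaves 7, 6, 5 or 1 day missing. The first full window is at Day 35.

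**3. Can a short window miss a menses?**

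A window of *w* consecutive days is certain to contain a menses onset only if the cycle is no longer than *w* days. A 28-day window can therefore miss the onset for eligible cycles of 29 to 38 days, and a 34-day window for 35 to 38 days. A full 35-day window can miss it only for 36 to 38 days. The mismatch widens an existing weakness; it does not create it. Passing is possible, not assured, because loss from a menses still under way on Day 1 could also count.

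**4. The clocks**

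The failure rule counts leaving the study; the window counts days on treatment. Take a last dose on Day 20. Section 4.6 schedules a Follow-up visit about 30 days after the last dose, near Day 50. Read literally, she may not have left the study before Day 28, yet she has only 20 treated days.

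**5. The floating window**

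A stop at Week 10 (Day 70) gives a window of Days 36 to 70, ending 24 − 10 = 14 weeks before Week 24.

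**6. Size, as illustration**

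Suppose a share *d* of each arm stops after Week 4 and would otherwise respond at the arm's planning rate. Recoding all of them as failures gives 0.55(1 − d_A) and 0.25(1 − d_C). At equal *d* the difference falls by 0.30·d.

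| Late drop-out A / C | Rates A / C | Difference | Power |
|---|---|---|---|
| 10% / 10% | 49.5% / 22.5% | 27.0 | 99.6% |
| 15% / 15% | 46.75% / 21.25% | 25.5 | 99.3% |
| 20% / 20% | 44.0% / 20.0% | 24.0 | 98.8% |
| 20% / 10% | 44.0% / 22.5% | 21.5 | 96.1% |
| 30% / 10% | 38.5% / 22.5% | 16.0 | 80.4% |
| 10% / 20% | 49.5% / 20.0% | 29.5 | 99.9% |

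Responders who depend on the rule number 130 × 0.10 × 0.55 ≈ 7 in Group A and 130 × 0.10 × 0.25 ≈ 3 on placebo at 10%, and about 14 and 6 to 7 at 20%. The direction reverses if placebo late drop-out exceeds 0.55/0.25 = 2.2 times that of Group A.

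If only a fraction *f* of late drop-outs, the same in both arms, is recoded because of the reason for stopping, the fall is f × 0.30·d, which is smaller than in the equal-drop-out rows.

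**The case against.** The strongest reply is that scoring the last 35 days of treatment is the protocol's consistent definition, in Section 3, the synopsis and Section 9.3.1. On that view, 24 weeks describes the regimens compared, and scoring women on their own last treated days is a choice of estimand. The protocol also has a bleeding endpoint anchored at Week 24 (change from baseline, Section 9.3.2), a Per-Protocol analysis, sensitivity imputations and an SAP that may add rules.

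Much of this stands for the floating window. A reader might infer that the rule demonstrably inflates the treatment difference. The documents do not show that: the distance from a drop-out-equals-failure rule is partly the distance between two estimands.

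A reader might also apply the phase 2 rate of about 84% and reach 0.20 × (0.84 − 0.25) = 11.8 points. That rate is a pictorial-chart score under 10 over Weeks 6 to 12 on monotherapy (Section 2.2.4.2), a different measure and regimen, so it cannot be assigned to drop-outs here.

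Nor do the documents establish that relugolix drop-outs would mostly pass. In phase 2, menstruation-related adverse events came mainly in the first 28 days, so for stops on Days 28 to 34 the direction of error is unclear. Intolerance is not hidden either, since Section 9.4 reports discontinuations due to adverse events.

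The reply does not remove the mismatch. Both numbers are fixed in Section 9.3.1 itself, so this is a stated rule that can misclassify, not detail left for later.

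**Conclusion.** The point holds, as a should-fix. The mismatch between 28 and 35 days, and between study and treatment, is an inconsistency within one section. It concerns stops in one seven-day interval, plus women whose treatment and study end dates differ; the number affected cannot be derived from the protocol.

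The floating window is a real gap between the 24-week objective and the scoring rule, but partly a choice of estimand, and a late drop-out *can* be a responder rather than *is* one. At equal late drop-out of 10% to 20%, and response at the planning rates, recoding every late drop-out lowers the 30-point difference by at most 3 to 6 points and leaves power at 98.8% or more. The effect is smaller if only listed reasons are recoded equally in both arms. It is larger if drop-out is concentrated in Group A: at 30% v 10% the difference is 16.0 points and power 80.4%. All drop-out rates are assumptions. The SAP was not available for this check and may already add rules for later drop-outs.

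**What to change.** 1. In Section 9.3.1, make failure depend on stopping study treatment before 35 days of treatment are complete. This aligns the cut-off with the window and puts both on the treatment clock.
2. Pre-specify as non-responders the women who stop study drug before Week 24 for an adverse event, for lack of efficacy, or for surgery or other therapy for fibroid bleeding. Do this in the primary analysis, or at least in a named key sensitivity analysis, and report the other scoring alongside.
3. State how women who stop for other reasons, such as withdrawn consent or loss to follow-up, are scored, since item 2 leaves them on their early window.

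The cost is a few sentences in Section 9.3.1 and the SAP before unblinding. No new data are needed, because the reason for early discontinuation is already recorded (Sections 10.1.6 and 10.1.7). Response rates would be slightly lower and there would be slightly more analysis work.

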9.3.2. Secondary Endpoint Analyses

The secondary endpoints are listed below:

- Proportion of women in the relugolix Group B versus the placebo Group C who achieve a menstrual blood loss volume of < 80 mL AND at least a 50% reduction from baseline menstrual blood loss volume over the last 35 days of treatment, as measured by the alkaline hematin method.

The following secondary endpoints will be assessed comparing each relugolix treatment group to placebo inferentially and relugolix Group A to Group B descriptively:

- Time to achieving a menstrual blood loss volume of < 80 mL AND at least a 50% reduction from baseline menstrual blood loss volume as measured by the alkaline hematin method;
- Change from Baseline to Week 24 in menstrual blood loss;

- Proportion of women who achieve amenorrhea over the last 35 days of treatment as measured by the alkaline hematin method;
- Time to amenorrhea as measured by the alkaline hematin method;
- Proportion of women with a hemoglobin below the lower limit of normal at Baseline who achieve an increase of ≥ 1 g/dL from Baseline at Week 24;
- Change from Baseline to Week 24 in the Menorrhagia Impact Questionnaire Score for physical activities;
- Change from Baseline to Week 24 in the Menorrhagia Impact Questionnaire Score for social and leisure activities;
- Proportion of women who achieve a mean Numerical Rating Scale score for uterine fibroid-associated pain over the last 35 days of treatment that is at least a 30% reduction from Baseline in the subset of women with a maximum pain score ≥ 4 during the 35 days prior to randomization;
- Change from Baseline to Week 24 in uterine volume; and
- Change from Baseline to Week 24 in uterine fibroid volume.

The analysis methods used for the primary endpoint will be applied to the analyses of the secondary endpoints of proportion of patients who achieve both a menstrual blood loss volume of < 80 mL AND at least a 50% reduction in menstrual blood loss volume over the last 35 days of treatment compared between relugolix Group B and placebo Group C, the proportion of patients with amenorrhea over the last 35 days, the proportion of women with a hemoglobin below the lower limit of normal at Baseline who achieve an increase of at least 1 g/dL at Week 24 and the proportion of women who achieve a mean Numerical Rating Scale score for uterine fibroid-associated pain over the last 35 days of treatment that is at least a 30% reduction from Baseline in the subset of women with a maximum pain score ≥ 4 during the 35 days prior to randomization.

For the secondary endpoints of time to achieving a menstrual blood loss volume of < 80 mL AND at least a 50% reduction from baseline menstrual blood loss volume and time to amenorrhea, time to event will be defined as weeks from randomization to first occurrence of the event as assessed by the alkaline hematin method. Patients without an event will be censored at last assessment date prior to the end of study. Kaplan-Meier methods will be used to describe the time to event distributions and stratified log-rank test will be used to compare each relugolix arm to placebo. Randomization stratification factors will be used to stratify inferential testing.

Descriptive statistics will be provided for changes in menstrual blood loss, hemoglobin, Numerical Rating Scale score for uterine fibroid-associated pain, uterine volume, and uterine fibroid volume baseline. The between treatment comparisons will be performed using model derived least squares means with treatment, stratification factors, baseline result accounted for in the model.

Baseline Numerical Rating Scale score is defined as the average Numerical Rating Scale score from the 35 days of data collected prior to the date of first dose of study drug after randomization. The Numerical Rating Scale score during the final study month is the average Numerical Rating Scale score during the last 35 days on treatment.

Details on the endpoint analyses including derivations, handling of missing data, and statistical methods will be provided in the SAP.

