6.2. Screening Period

Patients should have a diagnosis of uterine fibroids and a history of heavy menstrual bleeding with or without associated pain on a background of generally regular menses (ie, regularly occurring menstrual periods of \leq 14 days duration with a cycle of 21 to 38 days from the start of one menstrual period until the start of the next menstrual period) as reported by the patient for at least 3 months prior to the Screening 1 visit.

The screening period consists of the Screening 1, 2, 3, and 4 visits.

See [Figure 4-2](#) for details of the timing of the screening period visits as well as details of the feminine product dispensation and collection during screening. The Screening 4 visit should be skipped if the menstrual blood loss is \geq 160 mL in the first screening cycle.

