6.2.3. Screening 3 Visit

The patient will return for the Screening 3 visit if her menstrual blood loss from cycle 1 is ≥ 80 mL and within ≤ 15 days after the Screening 2 visit. At the Screening 3 visit, review of inclusion and exclusion criteria will be conducted confirmation of continued eligibility. Concomitant medication and adverse events will be assessed and vital signs taken. A signs and symptoms directed physical examination, a 12-lead ECG and a urine pregnancy test will be performed. At this visit, review the endometrial biopsy results and review mammogram results, if available. Confirm that the bone densitometry scans have been submitted for central reading. The mammogram and central bone densitometry results must be available prior to randomization.

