6.7.1.6. Patient Diary

All women enrolled in the study will be provided with a device with an application for a patient eDiary, along with detailed instructions for its use. Patients will complete daily eDiaries including compliance with study treatment, menstrual bleeding, use of feminine products, uterine fibroid-associated pain, and use of pain medication (analgesics) to treat uterine fibroid pain (see [Appendix 2](#)).

Queries will be handled by the vendor managing the eDiary data through the clinical site. The eDiary data will be reviewed by the investigator to identify any potential adverse events.

Patients will also receive a paper diary to enter information on menstruation status and feminine product use starting with Screening 1 visit and ending when they receive their eDiary at the Screening 3 visit.

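### The pain baseline and pain subset need 35 pre-dose days of scores, but pain scoring starts at Screening 3, so women who qualify on one cycle probably have only about 1 to 3 weeks

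*Protocol*

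**What the plan says.** - **Baseline.** Section 9.3.2: "Baseline Numerical Rating Scale score is defined as the average Numerical Rating Scale score from the 35 days of data collected" before the date of first dose. The on-treatment value is the average over the last 35 days on treatment.
- **Subset.** The 30% responder endpoint is evaluated "in the subset of women with a maximum pain score ≥ 4 during the 35 days prior to randomization".
- **Where pain is recorded.** Section 4.1, Section 6.7.1.6 and Appendix 2 place the Numerical Rating Scale (NRS) for fibroid pain in the eDiary. Before the device is issued, Section 6.7.1.6 provides for a different record: "Patients will also receive a paper diary to enter information on menstruation status and feminine product use". Pain is not among the listed paper items. The same section has this paper record begin at the first screening visit, "ending when they receive their eDiary at the Screening 3 visit".
- **When Screening 3 happens.** Screening 2 follows the end of the first screening menses by up to 5 (+2) days (Section 6.2.2). Screening 3 waits for the blood-loss result of that cycle and takes place "within ≤ 15 days after the Screening 2 visit" (Section 6.2.3).
- **One-cycle route.** Section 6.2: "The Screening 4 visit should be skipped if the menstrual blood loss is" at least 160 mL in the first screening cycle. Section 6.2.4 repeats this.

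**The concern.** The first screening menses is over before the pain diary exists, so it is never scored for anyone. A woman on the two-cycle route gets a second screening menses and a further cycle of eDiary entries. A woman on the one-cycle route does not, yet the same 35-day definition applies to her.

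Two things follow. First, the maximum score that admits her to the pain subset is taken over a short stretch that may lie mostly between periods. Second, her baseline mean covers fewer days, with a different share of menses days, than the full 35-day mean it is compared with. Where pain follows menses, both the denominator of the responder endpoint and the percentage reduction depend partly on when Day 1 fell in the cycle. The endpoint is tested for each relugolix group against placebo.

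**Working it through.** **Formula.** Count the onset of the first screening menses as day 1. Let D be menses duration, a the days from the end of menses to Screening 2, g the days from Screening 2 to Screening 3, C the cycle length, and b the day of the next menses on which dosing starts. Scored days before first dose are:

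- one-cycle route: N = (C + b) − (D + a + g)
- two-cycle route: N = (2C + b) − (D + a + g)

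**Inputs.** From the protocol: C = 21 to 38 and menses of at most 14 days (Section 4.3.1), a = 0 to 7 (Section 6.2.2), g at most 15 (Section 6.2.3). Assumed: D of at least 3, g of at least 1 (or 3 where stated), and b = 1 to 4. The value of b comes from the Schedule of Activities shown, which belongs to the earlier protocol version that required two cycles. The grids weight all combinations equally and are not a patient distribution.

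**The 35-day figure on the two-cycle route.** At C = 28, D = 6, a = 4, g = 8, b = 3: N = 56 + 3 − 18 = 41. Over D = 5 to 7, a = 0 to 7, g = 3 to 15, b = 1 to 4, the median is 40 days and 87% of combinations reach 35. At C = 26 it is 61%, and at C = 30 it is 99%. The window broadly fits this route.

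**One-cycle route.**

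- Same mid-window inputs: N = 28 + 3 − 18 = 13, which is 22 days short.
- C = 28, same ranges: median 12, 5th to 95th percentile 4 to 20, never 35.
- All feasible combinations (C = 21 to 38, D = 3 to 14, g = 1 to 15): median 13; 67% lie in 7 to 21 days, 19% below 7 and 13% above 21; 0.06% reach 35.

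**Sensitivity to text in the earlier version (C = 28, D = 5 to 7).**

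- Dosing the day after the next menses ends: N = 29 − a − g, from 29 − 7 − 15 = 7 to 29 − 0 − 1 = 28.
- Pain entries from Screening 2: N = (28 + b) − (D + a), from 29 − 14 = 15 to 32 − 5 = 27.

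Neither reaches 35.

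**Scored menses days.** With dosing on day b, at most b − 1 days of the new menses are scored, so 0 to 3 for b = 1 to 4. With dosing after that menses ends, all of it is scored.

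**What this can do to one woman (assumed: NRS 6 on 5 menses days, 0.5 otherwise, 28-day cycle, pain unchanged throughout).** A final 35-day window with one menses has mean (5×6 + 30×0.5)/35 = 1.29.

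- 12 scored days, none on menses (b = 1): mean 0.5, maximum 0.5. She is left out of the subset.
- 12 scored days, 3 on menses (b = 4): mean (3×6 + 9×0.5)/12 = 1.88, maximum 6. She enters, and 1 − 1.29/1.88 = 31% makes her a responder with no change. The final window holds only five menses days in 17 of the 28 possible phases (61%). If it holds two full menses its mean is (10×6 + 25×0.5)/35 = 2.07, and she is not a responder.
- A full 35-day baseline with b = 4 holds 5 + 3 = 8 menses days: mean (8×6 + 27×0.5)/35 = 1.76. The largest apparent reduction is 1 − 1.29/1.76 = 27%, so she is not a false responder in any phase.

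**The case against.** **Day 1 timing is not in the current text shown.** This stands. The synopsis and schedule of the current version are absent and Figure 4-2 is missing. The earlier version conflicts with itself: its schedule places Day 1 within 4 days of menses onset, while its Section 6.2 aims for about when the next menses finishes. Screening may last up to about 13 weeks (Section 4.1), so Day 1 could slip by a cycle, which would lengthen the diary. A reader might infer that no one-cycle woman ever has a complete scored menses. The documents do not support that; it depends on the Day 1 rule.

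**The SAP can average whatever is available.** Section 9.3.2 leaves derivations and missing data to the SAP, and a minimum-days rule belongs there. But no rule recovers scores that were never collected, and the start of the diary is a protocol matter.

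**The problem arises before randomization.** This also stands. The baseline window and subset are fixed before dosing in a blinded, stratified trial, so the shortfall should not unbalance the arms, and under no treatment effect both arms are affected alike. A reader might infer that Day 1 timing decides the responder endpoint as much as treatment does. Nothing here measures one against the other, and the share of women on the one-cycle route is not given.

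**Conclusion.** The point holds in a limited form. The definitions of baseline pain and of the pain subset require 35 pre-dose days of NRS scores, and the diary start does not supply them for women who qualify on one cycle. If Day 1 falls at about the next menses, they have about 1 to 3 weeks of scores (median about 12 to 13 days, almost never 35) against a full 35 days on treatment. Both alternative timings in the earlier version leave them short as well. How much menses is scored depends on Day 1 and may be little or none.

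The consequences are possible misclassification of entry to the pain subset and a baseline that is not comparable with the final mean. Their size also depends on how closely pain follows menses, which is assumed in the illustration. One secondary endpoint is affected; the primary endpoint is not. It is worth correcting because uncollected scores cannot be recovered later.

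**What to change.** Add the daily 0 to 10 pain item to the paper diary already issued at Screening 1 (Section 6.2.1), or dispense the eDiary at Screening 1, and amend Section 6.7.1.6 to match. The first screening menses is then scored, and the 35-day window can be filled on both routes. On the one-cycle route at least C + b − 1 days are scored, which is 28 + 3 − 1 = 30 in the mid-window case, and 35 once Screening 1 falls 5 or more days before that menses.

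Leave any minimum number of scored days to the SAP, and do not require a complete menses. A 35-day look-back from b = 1 misses the onset of the previous menses when the cycle is 36 to 38 days, so such a rule could drop eligible women because of cycle length.

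The cost is an amendment sentence and either a slightly longer paper diary during screening, with paper and electronic scores mixed in one baseline, or devices issued to women who then fail screening. The screen-failure rate is not given, so the number of extra devices cannot be stated.
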